ACE, Resilience, and Substance Use Disorder: Maternal and Baby Outcomes in the First Year of Life

Investigator: [name], MD

Co-Investigators: [name], [name], [name], MS, PhD, MBA, [name], MA

2/19/2020

1. Objective/ Purpose

The purpose of this study is to understand the maternal factors that contribute to the health of an infant born to a mother with substance use disorder (SUD). We will evaluate whether or not the outcomes of maternal and baby health can be identified early through maternal screening tools, including the Adverse Childhood Experience (ACE) questionnaire and the 7Cs Resiliency Tool.

2. Hypothesis

Mothers with SUDs that have higher maternal ACE scores will have children with poor outcomes, including difficulty reaching developmental milestones, poorer adherence to vaccination schedule guidelines, and more frequent ER visits in the first year of life. However, high maternal resilience scores may counter the high ACE scores and allow for improvement of poor health outcomes in these populations.

3. Background

Adverse Childhood Experiences (ACEs) are traumatic or life-threatening events that occurred to an individual during the ages 0-17 and are measured with the ACE Score questionnaire. These experiences include being a victim of physical and sexual abuse, neglect, and exposure to household dysfunction such as parental substance abuse or incarceration¹. Multiple studies have shown that the number of ACEs an individual experiences correlates with his or her risk in developing chronic health issues such as diabetes, asthma, and hypertension later in life²⁻⁴. In addition, ACEs correlate with a higher risk of engaging in risky behaviors such as substance use⁵.

A recent survey conducted by the Substance Abuse and Mental Health Services Administration (SAMHSA) showed that 5.4% of pregnant mothers had used illicit drugs including marijuana, opioids, and cocaine in the past month⁶. Moreover, ACE scores of pregnant women have been linked to poor coping mechanisms such as illicit drug use during pregnancy⁷. These scores also impact prenatal,

perinatal, and post-natal health⁸. For example, babies who were exposed to opioids in utero had significant associations with poorer health outcomes and delays in developmental stages⁹. Another study concluded that mothers suffering from substance use disorder engage in poor parenting practices such as “limited or absent parental monitoring and lower levels of parental involvement.”¹⁰ Currently, many medical practices are using ACE scores as a general screening tool to help identify health risks and provide individualized care and family support¹¹. Recent studies show that identifying positive childhood experiences is important when evaluating the impact of ACEs. Protective factors, such as resilience, can offset the negative health impacts of trauma^{12,13}. Described as good outcomes in the face of a threat to wellbeing¹³, resilience can be quantified by using a questionnaire called the 7Cs tool¹⁴. The 7Cs tool, which examines an individual’s competence, confidence, character, connection, contribution, coping and control, is a valid method to measure resilience. Currently, the 7Cs tool is internally validated for adolescents that have experienced trauma, and it has shown a correlation between better outcomes with a higher resilience score despite having higher ACE scores. Overall, there is limited information regarding ways to identify and determine the health impact of maternal resilience. More research is necessary to understand how ACEs and resilience affect postpartum outcomes in mothers with SUD and their child.

Significance of the Research

Currently, little research has been conducted to study the relationship between ACEs and maternal resilience and the health outcomes of mothers with SUDs and their newborn baby. Understanding factors that show a strong correlation with maternal and fetal health outcomes would allow health care providers to identify risks earlier, offer prenatal interventional care, and provide tailored resources for mothers and their infant.

4. Study Design

This is a prospective observational study that will require the initial administration of both the ACEs questionnaire and 7Cs resilience tool, followed by one year of chart reviews and/or phone calls to follow-up with patients regarding the identified outcome measures.

5. Proposed research Plan

A. Subjects

Number of subjects: 100

Inclusion criteria: Pregnant mother past her 1st trimester of pregnancy who is being seen at Cooper University Hospital Addiction Medicine clinic or Labor and Delivery or Maternal Fetal Medicine Unit. The subject is diagnosed with substance use disorder.

Exclusion criteria: Mothers under the age of 18.

Recruiting Methods: Subjects will be recruited through the Addiction Medicine clinic at Cooper Hospital. Staff at the clinic will ask any pregnant mothers, past their first trimester, if they are interested in participating in this study. Interested participants will be contacted by study co-investigators to learn more about the study. If all inclusion criteria is met, the pregnant woman will be invited to participate in the study.

Informed Consent Process: Prospective subjects will meet with either of the study co-investigators named earlier in the proposal. Additionally, prospective subjects may meet with the clinical psychologist on the study, [name]. All subjects will be given a copy of the informed consent to read along with the study co-investigators. Potential subjects will be invited to a private room away from distractions and will be allowed adequate time to ask questions and read the consent forms.

Vulnerable Subjects: This study will include vulnerable subjects, namely pregnant women and their child.

Compensation to Subjects: No financial or other compensation will be offered to the subjects in exchange for participating in this study.

Treatment for Research-Related Injuries: No research-related injuries are anticipated in relation to participating in this study. If any research-related injuries are sustained during the course of this study, the subject may reach out to the research investigator or co-investigators to determine the appropriate course of action. While conducting ACEs and resilience interviews, re-traumatization will be a concern which would be handled by the current resources available through the Addiction Medicine clinic and Cooper Hospital.

B. Research Methods and Procedures

General description of methods and procedures: After consenting to participate in this study, pregnant mothers will be provided a modified survey based off of the Adverse Childhood Experiences (ACE)

questionnaire and 7C Resilience Tool. After giving birth, patient charts will be monitored for maternal commitment to treatment, child custody status, the number of times the child was admitted to the emergency room, adherence to recommended pediatric vaccination schedules, and infant developmental milestones. These measurements will be taken over the course of 1 year after child birth.

Summary of visit procedures: Pregnant mothers will meet with any of the co-investigators prenatally to complete the ACE questionnaire and 7C Resilience Tool. After the initial intake, outcome measures will be collected via chart review or verbally through phone call with the mother. Data will be collected at birth, 2 months, 4 months, 6 months, and 1 year after birth.

Procedures just for research purposes: The ACEs questionnaire and 7C Resilience Tool are not included in standard prenatal care and are solely being administered for research purposes. If the subjects were not enrolled in this study, the only difference in care would be the absence of either screening tool being administered prenatally.

How participation differs from standard of care/ study duration: As an observational study, participating subjects will be provided the appropriate standard-of-care.

Study Duration: Pregnant mothers will be enrolled between March 1, 2020 to August 1, 2020. All mothers will be followed for one year postpartum. The total duration of the project for the individual will be the duration of the pregnancy as well as the child's first year of life. This study will be conducted between March 1, 2020 - January 31, 2020.

Data Analysis Plan, Statistical Tests, and Sample Size Rationale

Outcome measures being followed at birth of baby, and at 2, 4, 6 and 12 months after birth:

1. Is the mother still parenting and have custody of the baby?
2. Is the mother receiving treatment for substance use disorder?
3. Has the baby reached expected developmental and health milestones after delivery?
4. How many Emergency Room visits did the baby have postnatally?
5. Does the child meet vaccination schedule as proposed by the CDC?

Sample size. The key outcomes of the study will include binary measurements (parenting, custody, continued treatment, etc.) measured at 2, 4, 6 and 12 months after birth. These outcomes will be related to the pre-natal scores of the ACE and 7C survey tools. Based on a repeated measures design, a sample size of 100 will provide >90% power to detect an odds ratio of 2 or greater for each standard deviation above the mean of the ACE scale (1-10) assuming a mean of 3.7 and a standard deviation of 2.7 and a response proportion of 0.50.

Data Analysis. The checking, assessment and analysis of the data will be carried out in a blinded fashion. Demographic and clinical characteristics will be presented using means with standard deviation for continuous variables and counts with proportions for categorical variables. The statistical analysis will be carried out using “intention-to treat” and “per-protocol” approaches. The primary outcomes (parenting, custody, continued treatment, etc.) will be analyzed using generalized estimating equations (GEE) appropriate for repeated measures over time. Odds ratios with 95% confidence intervals for the relationships of ACE and 7C with the clinical outcomes will be presented.

6. Risks and benefits

- A. Potential Risks due to Study Participation: No study treatments will be included in this observational study. However, in some cases, re-traumatization is a possibility and necessary resources will be made available to the subject.
- B. Minimizing Risks: Risks to subjects will be minimized by the study design, which is observational and not anticipated to be risky towards the mother or fetus. Subjects being seen at the Addiction Medicine clinic and Labor and Delivery Ward will have normal access to treatment and follow-up visits, which follows normal standard of care at Cooper Hospital.
- C. Potential Benefits: Potential benefits of this study would be increased adherence to substance use disorder (SUD) treatment, appropriate follow-up with pediatricians per recommended vaccination schedule, and identifying risk factors during pregnancy to initiate early intervention practices. Society may benefit from this research by understanding the risks of ACEs and resilience scores of pregnant mothers suffering from SUD and how it affects the care of their newborn child. The findings of this

study may benefit the resources and management of mothers with SUD during pregnancy and postpartum.

- D. Risk: Benefit Ratio: Due to the absence of risks associated with this study, the ratio of risks to benefits is reasonable to individual subjects and society.

7. Plans for Monitoring Subject Safety

Subjects are being enrolled in an observational study, there are no anticipated adverse events during the course of this study. However, in some cases, re-traumatization may be possible and necessary resources will be made available to the subject.

8. Procedures to Maintain Privacy and Confidentiality

All information obtained in this study will be strictly confidential, except, as may be required by law. Each mother and infant will be assigned a number and patient's name and identifying information with that number will be kept in a separate locked cabinet. We will use only the assigned number to the infants on the data sheet. All the files and records created for this study will be stored in [name] office at [name] and Cooper Hospital in a locked cabinet or in a computer with a password. Any publication resulting from this study will refer to the patient by a pre-assigned number. No published data will disclose the identity of any patient.

References

1. Center for Disease Control and Prevention. (2019, December 31, 2019). Preventing Adverse Childhood Experiences. Retrieved from https://www.cdc.gov/violenceprevention/childabuseandneglect/aces/fastfact.html?CDC_AA_refVal=https%3A%2F%2Fwww.cdc.gov%2Fviolenceprevention%2Fchildabuseandneglect%2Facestudy%2Faboutace.html
2. Bellis, M. A., Hughes, K., Leckenby, N., Hardcastle, K. A., Perkins, C., & Lowey, H. (2015). Measuring mortality and the burden of adult disease associated with adverse childhood experiences in England: a national survey. *J Public Health (Oxf)*, 37(3), 445-454. doi:10.1093/pubmed/fdu065

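### Odds ratios alone do not address the early-identification aim: the smallest effect the study is sized for implies an AUC of about 0.68, and no measure of discrimination is planned

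*Combined protocol and SAP*

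**What the plan says.** Section 1 (Objective/ Purpose) opens with an aim of understanding contributing maternal factors. It then says what will be evaluated: "We will evaluate whether or not the outcomes of maternal and baby health can be identified early through maternal screening tools", naming the ACE questionnaire and the 7Cs tool. The Significance of the Research paragraph gives the intended use: knowing which factors correlate strongly with outcomes "would allow health care providers to identify risks earlier, offer prenatal interventional care, and provide tailored resources". The Hypothesis (Section 2) is associational: higher ACE goes with poorer outcomes, and resilience may offset this.

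The planned output is in Section 5.B, Data Analysis. It consists of descriptive summaries, GEE models for the repeated binary outcomes, and this result: "Odds ratios with 95% confidence intervals for the relationships of ACE and 7C with the clinical outcomes will be presented". The document mentions no AUC, sensitivity, specificity, predictive value, cut-point or calibration.

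The Sample size paragraph is also about association: "a sample size of 100 will provide >90% power to detect an odds ratio of 2 or greater for each standard deviation" of ACE.

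**The concern.** An odds ratio per SD describes how the odds of an outcome shift with the score. It does not say how many mothers with the outcome the score would flag, or how many without it would be flagged wrongly. The second aim is a question of that kind.

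The study could find a clearly significant odds ratio and still leave open whether ACE or 7C is useful for picking out mothers at risk. The findings are meant to inform prenatal care and the allocation of resources, so a reader could take an association as evidence that screening works. The plan reports nothing that would show whether that step is justified.

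**Working it through.** **Inputs from the documents.**
- Sample size (Section 5.A): "Number of subjects: 100".
- Odds ratio (Section 5.B, Sample size): 2 or greater per SD of ACE.
- ACE distribution (same paragraph): "the ACE scale (1-10) assuming a mean of 3.7 and a standard deviation of 2.7".
- Outcome rate (same paragraph): "a response proportion of 0.50".
- Repeated outcomes (same paragraph): "measured at 2, 4, 6 and 12 months after birth", so four occasions.

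**Assumptions.** Two-sided alpha of 0.05, which the documents do not state but which matches the 95% intervals. Standard-normal ACE score, with a discrete score as a check. Within-mother correlation is not stated, so a range is used. No dropout.

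**1. The plan's own figure.** For logistic regression on a continuous covariate:

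power = Φ(√(N·p·(1−p))·ln OR − 1.96) = Φ(√(100 × 0.25) × 0.693 − 1.96) = Φ(1.506) = 93.4% at one time point.

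With four measures, the effective sample size is 400/(1 + 3r). At r = 0.5 this is 160 and power is 99.2%. At r = 0.9 it is 108.1 and power is 95.0%. The stated figure of more than 90% therefore reproduces. A stricter Wald formula gives 84.6% at one time point and passes 90% with four measures once r is below about 0.8. Simulation of one time point gives 89% (Wald) and 90% (likelihood ratio).

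**2. Discrimination implied by that effect.** Take logit P(Y = 1 | x) = x·ln 2 with x standard normal, so the outcome rate is 0.50. The AUC is the probability that a randomly chosen mother with the outcome scores higher than one without it.

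| Calculation, OR 2 per SD, outcome rate 0.50 | AUC |
|---|---|
| Normal score, numerical integration | 0.679 |
| Binormal approximation, Φ(0.693/√2) = Φ(0.490) | 0.688 |
| Discrete score 1–10, mean 3.7, SD 2.7 (beta-binomial) | 0.676 |
| Discrete score 0–10, same mean and SD | 0.682 |

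At assumed outcome rates of 0.1 to 0.3 the AUC stays between 0.68 and 0.69.

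**3. Classification at the same effect.** For a cut at the median of the normal score, sensitivity = 2∫φ(x)/(1 + e^(−x·ln 2)) dx over x > 0, which is 0.629. By symmetry specificity is also 0.629, so 1 − 0.629 = 37% of mothers are misclassified. On the discrete scores the best single cut is ACE of 4 or more, with sensitivity 0.57–0.62 and specificity 0.66–0.71.

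**4. Larger effects (normal score, outcome rate 0.50).** OR 3 gives an AUC of 0.756 and OR 4 gives 0.798.

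**5. Precision of an AUC at n = 100.** The Hanley–McNeil formula is

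SE² = [A(1−A) + (n₁−1)(Q₁−A²) + (n₀−1)(Q₂−A²)]/(n₁n₀), with Q₁ = A/(2−A) and Q₂ = 2A²/(1+A).

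With A = 0.68: A(1−A) = 0.2176, A² = 0.4624, Q₁ = 0.5152, Q₂ = 0.5505.
- 50 with and 50 without the outcome: SE² = (0.2176 + 2.585 + 4.316)/2500 = 0.00285, SE = 0.053, 95% interval about ±0.10 (0.58 to 0.78).
- 20 and 80 (20 events is an assumed figure): SE² = (0.2176 + 1.002 + 6.958)/1600 = 0.00511, SE = 0.071, 95% interval about ±0.14 (0.54 to 0.82).

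**The case against.** The strongest reply is that the study is associational. The first stated purpose, the Hypothesis and the Significance paragraph all speak of factors, relationships and correlation. Read with them, identifying outcomes early could mean only that a prenatal score is associated with later outcomes. That stands in part: odds ratios suit those aims, and it would be wrong to infer that the planned analysis fails the study's purpose as a whole. The evaluation sentence remains, however. It names screening tools, and its natural reading goes beyond association.

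A reader might infer three stronger points that the documents do not support.
- *That the study is built around a poor tool.* The plan says 2 or greater, so 0.68 is the value at the lower bound, for ACE alone at one time point, and not a forecast. The documents set no threshold for poor discrimination. The AUC of ACE and 7C together cannot be derived from them.
- *That positive predictive value would be low.* This needs an outcome rate below 0.50, and 0.50 is the only rate the plan gives.
- *That the investigators will present a significant odds ratio as successful screening.* The plan says only that odds ratios will be presented.

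It is also fair that an AUC from 100 mothers is imprecise. With 20 events the interval runs from near chance to above 0.80. That argues for descriptive estimation rather than a test. It does not argue for omitting the estimate, since a wide interval would itself restrain overclaiming.

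**Conclusion.** The concern holds as a gap in reporting against one of the two aims in Section 1. The GEE odds ratios are a valid answer to the association aim, and the sample-size figure reproduces. They do not by themselves answer whether outcomes can be identified early. At the smallest effect the study is sized for, the score would separate mothers only moderately: AUC about 0.68 (0.676 to 0.688 across score models at an outcome rate of 0.50), and 63% sensitivity and specificity at the median. These figures rest on an odds ratio of exactly 2, ACE alone, one time point and the assumed score distribution. The median cut is illustrative, because the protocol sets none. A significant odds ratio is compatible with this level of separation, so it should not alone carry a conclusion on early identification.

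**What to change.** Keep the GEE odds ratios as the main analysis. Add the following to Data Analysis:

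- For each binary outcome at 12 months, report a descriptive AUC with bootstrap 95% confidence interval for ACE, for 7C and for both together, with optimism correction for the combined model.
- Report sensitivity and specificity at one cut-point fixed before analysis. If no external cut-point is adopted, the rule could be the sample median.
- State that any conclusion on early identification rests on these estimates and their intervals.

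If these measures are not wanted, reword the evaluation sentence in Section 1 and limit the conclusions to association. Either change removes the mismatch.

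The cost is a few lines of text and code, because the scores and binary outcomes are already being collected. The downsides are wide intervals (about ±0.10 for the AUC with 50 events, about ±0.14 with an assumed 20, and wider with loss to follow-up) and possibly a less favourable headline. Emergency room visits are a count, so they fall outside these measures unless a binary version is defined.

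### Three units are eligible but a recruitment route is described for only one, the addiction clinic, and treatment status at entry is not recorded although treatment is a primary outcome

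*Combined protocol and SAP*

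**What the plan says.** - **Eligibility (5.A, Inclusion criteria).** A pregnant woman past the first trimester qualifies if she is one "who is being seen at Cooper University Hospital Addiction Medicine clinic or Labor and Delivery or Maternal Fetal Medicine Unit". The clinical requirement is a diagnosis: "The subject is diagnosed with substance use disorder". Being in treatment is not required.
- **Recruitment (5.A, Recruiting Methods).** "Subjects will be recruited through the Addiction Medicine clinic at Cooper Hospital". The approach is made there: "Staff at the clinic will ask any pregnant mothers, past their first trimester, if they are interested in participating in this study". The co-investigators handle later contact and consent. No approach is described for the other two units.
- **Minimizing Risks (6.B).** "Subjects being seen at the Addiction Medicine clinic and Labor and Delivery Ward will have normal access to treatment and follow-up visits". This names two of the three units.
- **Outcome 2 (5.B, outcome list).** "Is the mother receiving treatment for substance use disorder". The Sample size and Data Analysis paragraphs list continued treatment among the key and primary outcomes.
- **Target population (section 2).** "Mothers with SUDs that have higher maternal ACE scores will have children with poor outcomes". Neither this hypothesis nor the expected benefit in 6.C is limited to women attending an addiction clinic.

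**The concern.** A site following Recruiting Methods as written would have no procedure for a woman seen only in Labor and Delivery or Maternal Fetal Medicine, although she meets the inclusion criteria. The sample would then consist of women who already attend an addiction clinic.

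Two things are at stake. The first is the population to which the results apply: the hypothesis and expected benefit speak of mothers with SUD without restriction, while the described route reaches a subset defined by contact with addiction services. The second is the meaning of outcome 2. If entry depends on something close to treatment, a positive answer after birth may mean that a woman stayed in treatment or that she began it. These are different questions, and ACE and 7C scores may relate to them differently. Without status at enrolment, the analyst cannot tell them apart.

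**Working it through.** The point concerns design, so the main check sets the texts side by side.

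**1. Units named in each place**

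| Place | Addiction Medicine | Labor and Delivery | Maternal Fetal Medicine |
|---|---|---|---|
| 5.A Inclusion | yes | yes | yes |
| 5.A Recruiting Methods | yes | no | no |
| 6.B Minimizing Risks | yes | yes | no |

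The three lists differ. The entry in 6.B does not establish a second route, because a clinic patient may also be seen on the ward. It does prevent a reader from concluding that clinic-only entry was intended.

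**2. What outcome 2 measures**

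Let w be the proportion of mothers in treatment at enrolment, r the probability that such a mother is in treatment at a given follow-up (retention), and u the same probability for a mother not in treatment at enrolment (uptake). The observed proportion is

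P = w·r + (1 − w)·u.

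Only P is observed if w is not recorded, so r and u cannot be recovered. The same holds for the odds ratio on ACE or 7C: if the score is related to w, the estimate mixes its relation with entry status and its relations with retention and uptake. Clinic-only recruitment would not by itself fix w at 1, because the documents do not say that attending the clinic means receiving treatment.

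**3. What is recorded**

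Section 5.B names the ACE and 7C tools at intake, then outcomes at birth and at 2, 4, 6 and 12 months. Neither recruiting unit nor treatment status at enrolment is named. The birth assessment is the earliest look at outcome 2, and for a woman enrolled soon after the first trimester it comes months after entry.

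**4. The stated power**

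Inputs from the Sample size paragraph: N = 100, odds ratio 2 per standard deviation of ACE, response proportion 0.50. Two-sided alpha of 0.05 is assumed, in line with the planned 95% intervals. With the usual formula for a continuous predictor in logistic regression:

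- Single visit: Φ(√(100 × 0.50 × 0.50) × ln 2 − 1.96) = Φ(5 × 0.693 − 1.96) = Φ(1.51) = 93.4%.
- Four visits, within-mother correlation ρ (not given, so assumed): effective N = 100 × 4 / (1 + 3ρ). At ρ = 0.9 this is 108 and power is 95.0%. At ρ = 0.5 it is 160 and power is 99.2%.

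A simulated single-visit logistic regression (2,000 runs) gave about 88.6%, so at one visit the claim is borderline. The plan, however, bases its power on repeated measures. The stated figure is therefore not in error on its own inputs.

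**The case against.** The strongest reply is that this is a wording gap. The recruiting text does not say that the clinic is the sole route, and 6.B points to a second unit. Every single-centre cohort has limited generalisability. Following women from prenatal clinic attendance to postpartum treatment is coherent and not circular, and the plan's own phrase, continued treatment, already suggests retention. The child outcomes in the hypothesis (milestones, vaccination, emergency visits) are not the variable on which women would be selected.

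Much of this stands, and it rules out several stronger readings that a reader might infer:

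- *That every mother enters through the treatment clinic.* This is one literal reading, and 6.B leaves it open.
- *That all enrolled mothers are already in treatment.* Clinic attendance is not equated with treatment anywhere.
- *That the results cannot apply to other mothers with SUD.* The association with ACE may be the same outside the clinic; the documents give no evidence either way. The supportable statement is that generalisation lacks a basis.
- *That power is lost because clinic attenders have a narrower ACE range.* The plan does not say which population its mean of 3.7 and standard deviation of 2.7 describe, gives no second standard deviation, and defines its effect per standard deviation.

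It is also fair that approaching women in Labor and Delivery may be difficult: both tools must be completed before birth, and consent calls for a private room and adequate time. Wider recruitment is therefore a choice for the investigators.

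The reply does not remove the differing lists of units. Nor does it supply entry status: outcome 2 is worded as current receipt in one place and continuation in another, while eligibility asks only for a diagnosis. The planned summary of clinical characteristics could include treatment status, but the plan does not say so.

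**Conclusion.** The point holds in a limited form and should be corrected. One of three eligible units has a described recruitment route, and the texts in 5.A and 6.B must be reconciled. On the literal reading, selection is on addiction-clinic attendance, so conclusions for mothers with SUD in general are unsupported. Whichever reading is right, retention and uptake cannot be separated in outcome 2 without treatment status at enrolment. The direct effect falls on one of the five listed outcomes; for the other four the issue is the population described. The documents contain nothing from which to quantify a bias, and no fault is found with the stated power. The conclusion assumes that no other recruitment procedure or data form exists outside this document.

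**What to change.** 1. **Make eligibility and recruitment agree.** Either (a) describe in Recruiting Methods how women in Labor and Delivery and Maternal Fetal Medicine are identified and approached, and how the tools and consent are completed before birth; or (b) limit inclusion to Addiction Medicine clinic attenders and restrict the hypothesis, expected benefit and conclusions to them. Align 6.B with the choice.
2. **Record two items at enrolment for every mother:** recruiting unit, and whether she is receiving SUD treatment.
3. **Analyse outcome 2 by enrolment treatment status.** Present it separately by status, or include status as a covariate in the GEE model and say that the odds ratio is then conditional on it. Call the outcome retention for women already in treatment at entry and uptake for the others. If one group is small, report its counts without a model.
4. **Use one name for outcome 2** across 5.B, Sample size and Data Analysis.

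Cost: two data fields and a short protocol edit. Option (a) adds work for staff in two units and has the feasibility limits noted above. Option (b) costs breadth of claim. Treatment status at enrolment may be hard to recover reliably later, so it is best collected from the first mother enrolled.

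### Does a study window that ends before it begins put the 12-month follow-up at risk?

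*Combined protocol and SAP*

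**What the plan says.** Section 5.B, Study Duration, first sets the recruitment period and the follow-up: "Pregnant mothers will be enrolled between March 1, 2020 to August 1, 2020. All mothers will be followed for one year postpartum". It adds that each participant is in the project for her pregnancy and the child's first year. The paragraph then closes with the study period: "This study will be conducted between March 1, 2020 - January 31, 2020". No other place in the document gives an end date.

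Follow-up is described in three further places, always relative to birth or as a length of time:

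- Section 4, Study Design: the questionnaires are "followed by one year of chart reviews and/or phone calls".
- Section 5.B, Summary of visit procedures: "Data will be collected at birth, 2 months, 4 months, 6 months, and 1 year after birth".
- The sample size paragraph: key binary outcomes "measured at 2, 4, 6 and 12 months after birth".

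Entry is open to a "Pregnant mother past her 1st trimester of pregnancy", which limits how much pregnancy can remain at enrolment.

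**The concern.** Taken literally, the study is over before it starts. The printed end also precedes the protocol's own date of 19 February 2020, and because the design is prospective it cannot be a retrospective data window. As the only calendar end date in the document, it looks like something a study team might have to work to.

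The more serious worry is a wrong repair. Someone who simply moves the year on by one would get 31 January 2021. If data collection really stopped then, no mother could have a 12-month assessment, and more than half would miss the 6-month one as well. The GEE analysis would lose its last time point entirely and much of the one before it.

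**Working it through.** **Inputs from section 5.B.** Printed window 1 March 2020 to 31 January 2020; enrolment 1 March to 1 August 2020; follow-up to one year after birth.

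**Assumptions, not in the document.** The first trimester ends at 12, 13 or 14 weeks; birth is at 37, 40 or 42 weeks; enrolment date and gestational age at entry (from that lower limit to birth) are uniform.

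**1. The printed window.** 31 January 2020 to 1 March 2020 is 30 days (2020 is a leap year). 1 March to 1 August is 153 days, so the printed end precedes the close of enrolment by 30 + 153 = 183 days. The printed window cannot be reproduced as a valid period.

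**2. Year read as 2021.** 1 March 2020 to 31 January 2021 is 336 days, less than a year. A mother who enrols and delivers on the first day reaches 12 months on 1 March 2021, so 0 of 100 mothers could have the assessment in the window.

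For the 6-month assessment, birth must be by 31 July 2020, which is day 152 counting 1 March as day 0. On a grid of 154 enrolment days and 197 possible remaining-pregnancy days (entry from 12 weeks, birth at 40), the pairs that qualify number 153 × 154 / 2 = 11,781 out of 154 × 197 = 30,338, or 38.8%. So 61.2% miss it. Entry from 14 weeks gives 58.2%. Over births at 37 to 42 weeks the range is 52.8% to 63.7%.

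**3. Year read as 2022.** The window is 336 + 365 = 701 days. For the last enrolee:

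latest 12-month date = 1 August 2020 + (weeks at birth − weeks at entry) + 1 year

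| Entry | Birth at 37 weeks | Birth at 40 weeks | Birth at 42 weeks |
|---|---|---|---|
| 12 weeks | 23 Jan 2022 | 13 Feb 2022 | 27 Feb 2022 |
| 13 weeks | 16 Jan 2022 | 6 Feb 2022 | 20 Feb 2022 |
| 14 weeks | 9 Jan 2022 | 30 Jan 2022 | 13 Feb 2022 |

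The largest overrun is 27 days. The share of mothers whose 12-month date falls after 31 January 2022 is 0% for birth at 37 weeks. For entry from 12, 13 and 14 weeks it is 0.30%, 0.07% and 0% with birth at 40 weeks, and 1.16%, 0.67% and 0.30% if every birth were at 42 weeks.

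**4. Does any statistical quantity use the date?** The power statement rests on n = 100, an odds ratio of 2 per standard deviation and a response proportion of 0.50. With a two-sided 5% level (assumed; the document gives none) and one measurement per mother:

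power = Φ(√(100 × 0.5 × 0.5) × ln 2 − 1.96) = Φ(3.466 − 1.960) = 93.4%

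This agrees with the stated figure of more than 90%, and no calendar date enters it. The GEE model is indexed by time since birth.

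**The case for a change.** The best argument for acting is that the error is certain, the date is the only one of its kind in the document, and the repair is one line. The obvious repair, adding a year, would also be wrong, so it is fair to say that the correct year should not be guessed. Even 31 January 2022 is tight for a mother enrolled on the last day at the earliest eligible week.

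The first part stands: the sentence is wrong, and 2021 would be no cure. The harm, however, does not come from the printed text. It needs a second mistake, one that collides with a sentence in the same paragraph: "All mothers will be followed for one year postpartum". Nobody can reconcile an 11-month study with that promise, so the figures for lost 6- and 12-month assessments describe a reading that the document already rules out.

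The tightness of 2022 concerns a rare corner case. Nothing in the document makes the end of the study period a cut-off for assessments, so a mother due a few days later would still be followed under the per-mother rule. A padded end date would rest on gestational limits that the document does not give.

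**Conclusion.** This is a clerical slip, and no change to the plan follows. The dates are impossible as printed, by 30 days, but the intended conduct is clear from the enrolment period, the birth-anchored schedule and the one-year follow-up, which agree wherever they appear. Correcting the year would leave the assessments, the sample size, the analysis and the conclusions as they are.

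31 January 2021 is incompatible with the rest of the paragraph. 31 January 2022 is broadly compatible, with at most about 1 mother per 100 reaching 12 months after it, and only if every birth were at 42 weeks. That figure depends on the assumed 12 to 14 week entry limit and uniform entry. The document does not state the intended year, so 2022 is an inference and only the investigator can confirm it. The conclusion does not depend on it, because follow-up is governed by each birth and not by the study's closing date.
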